## **7.6 Termination Criteria On Statistical Grounds**

This section does not apply as there is no interim analysis and evaluation in this trial.

## **7.7 Statistical methods for all data, together with missing, unused or incorrect data (including dropouts and withdrawals) and processing methods for unreasonable data**

All subjects shall be included in the analysis of primary indicators, and the data from the full analysis set and the per-protocol set shall be selected respectively for the analysis. When the analysis conclusions of the above two data sets are consistent, the credibility of the study results can be enhanced.

For any missing data that may appear during the study process, all analyses will be based on the actual data obtained. Any filling in the missing primary endpoint indicators will be addressed in the statistical analysis plan.

Incorrect and unreasonable data will be dealt with in the data cleansing process prior to statistical analysis. For dropouts and withdrawals from the trial, the information of these patients will still be included in the final statistical analysis. All specific reasons for dropouts and withdrawals will be explained in detail in the statistical report.

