### 6.1.3 Measures to reduce and avoid bias

- (1) The investigators participating in this study will receive training on the clinical trial protocol and the operating procedure for the investigational medical device, and strictly abide by the inclusion and exclusion criteria.
- (2) The sponsor will assign a qualified clinical trial monitor to monitor the study center, make quality control and monitoring records, and communicate with the investigators in time about the problems found during the monitoring.
- (3) Interventions will be performed on the subjects according to the randomization results obtained by the central randomization system.
- (4) Multi-center clinical study design is adopted to make the results more objective and reliable, and avoid data bias in single-center clinical study.
- (5) The subjects with good protocol compliance will be included as far as possible, and the subject's follow-up, withdrawal and dropout will be controlled during the clinical study period.
- (6) Fixed efficacy assessors will be arranged before and after treatment, who will receive training on strict efficacy assessment criteria to prevent detection bias.
- (7) To reduce data loss, data analysis will also be performed on subjects who withdraw from treatment.

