## **7.8 Procedure for reporting deviations from the original statistical plan**

The statistical analysis plan needs to be confirmed by the sponsor, coordinating investigators, data management and statistical analysis personnel, and finalized prior to database locking. Before finalization, the initial analysis plan can be modified according to the actual situation in the trial process. Any change to the original statistical analysis plan due to the changes in the protocol shall be confirmed again by the sponsor, coordinating investigators, data management and statistical analysis personnel, and the change shall be made in strict compliance with the clinical trial operating rules and procedures. In principle, no change will be made to the main analysis principles, methods, and analysis sets, and all changes (if any) shall be recorded.

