## **7.9 Selection criteria for subjects included in the analysis and the rationale**

**Full Analysis Set (FAS):** A set of subjects determined according to the Intention To Treat principle, which refers to a data set composed of all subjects who have signed an informed consent form and used the investigational medical device. For subjects whose primary efficacy evaluation is not observed, different strategies will be adopted to intercept the missing data.

**Per-Protocol Set (PPS):** refers to a subset of treatment population who have all finished the trial and have no severe deviation from the protocol (i.e., violations of subjects of the clinical trial against the inclusion criteria or exclusion criteria).

**Safety Set (SS):** refers to the set of all subjects who have signed an informed consent form, used the investigational medical device, and have at least one safety evaluation result.

Efficacy analysis will be performed based on the Full Analysis Set and Per-Protocol Set. All demographic analysis at baseline will be performed based on the Full Analysis Set, and the safety evaluation will be performed on the Safety Set.

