### **10.2.3 Analysis of risks regarding the subjects**

Since the investigational medical device has high requirements for early postoperative rehabilitation exercise, the early engagement of the subjects in postoperative rehabilitation exercise may lead to failure of the investigational medical device and AEs. At the same time, the excessive withdrawal of subjects due to the failure of the investigational medical device and AEs may also lead to the failure of the clinical trial. The investigational medical device is designed to be an innovative soft anchor, with small damage caused at implantation. The control device (Fast-Fix 360) is also a product that has been marketed abroad for many years and has been applied for clinical use in China for a certain number of years. Considering this, the subjects are expected to have good compliance, and the medical staff participating in the study will provide appropriate education on the precautions for postoperative rehabilitation for the subjects. As a result, the subjects are less likely to withdraw from the trial due to the failure of the investigational medical device postoperatively.

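### Observed-data analysis is the only concrete rule for a missing 6-month Lysholm score, and it could favour non-inferiority if failed repairs go missing more often in the investigational arm

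*Combined protocol and SAP*

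**What the plan says.** The combined protocol and SAP treats a missing 6-month score in several places.

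- Section 7.7 gives the working rule: "For any missing data that may appear during the study process, all analyses will be based on the actual data obtained". The next sentence defers imputation: "Any filling in the missing primary endpoint indicators will be addressed in the statistical analysis plan".
- Section 7.7 also wants every subject in the analysis of the primary indicator, and says of dropouts and withdrawals that "the information of these patients will still be included in the final statistical analysis". It does not say how a subject without a 6-month score enters a 6-month analysis.
- Section 7.9, under the FAS: "For subjects whose primary efficacy evaluation is not observed, different strategies will be adopted to intercept the missing data". No strategy is named.
- Section 6.1.3, item 7: "To reduce data loss, data analysis will also be performed on subjects who withdraw from treatment".
- Section 7.9 limits the PPS to subjects "who have all finished the trial and have no severe deviation from the protocol".
- Section 7.8 on the plan that is to settle the matter: "Before finalization, the initial analysis plan can be modified according to the actual situation in the trial process". Finalisation is due before database lock.

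The primary analysis (section 7.1.2) is an ANCOVA of the 6-month change from baseline, with the lower 95% limit compared with the margin. The combined document fixes no imputation method, missing-data assumption, rule for failed repair or reoperation before 6 months, or sensitivity analysis.

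**The concern.** These statements are not reconciled, and only the observed-data sentence can be carried out as written. Unless something is added, subjects without a 6-month score contribute nothing to the primary comparison.

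That matters if the loss is related to outcome, and the plan foresees that it may be. Section 10.2.3 names "the excessive withdrawal of subjects due to the failure of the investigational medical device and AEs" as a possible cause of trial failure, and section 13.1.3 lists study withdrawal, device removal and reoperation among adverse event outcomes. If failed repairs disappear from the investigational arm more than from the control arm, the observed difference moves towards zero, which in a non-inferiority trial is the direction of success.

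Agreement between FAS and PPS, which section 7.7 treats as adding credibility, would not reveal this. The PPS excludes non-completers by definition, and an observed-case FAS loses the same subjects. The 3-month Lysholm score, collected under the section 6.2.1 schedule, plays no part in the primary analysis.

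**Working it through.** **1. The plan's own figure.** Inputs from sections 7.2.1 and 7.3: SD 8, margin 5.1, true difference 0, one-sided alpha 0.025, power 80%. Then n = 2 × (1.960 + 0.842)² × 8² / 5.1² = 38.6, so 39 per group against the stated 40. For 15% dropout, 40 / 0.85 = 47.06, which gives the planned 47 per group. At the 20% dropout of section 7.4, 47 × 0.8 = 37.6; with 37 per arm, power is 78.3%. Loss of power is therefore not the main issue.

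**2. How observed-data analysis moves the estimate.** Let f be an arm's failure rate, c the points lost by a failure, w the share of failures with no 6-month score, and u the share of other subjects with none.

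- True difference: −c × (f_T − f_C).
- Failure share among observed subjects: g = f(1 − w) / [f(1 − w) + (1 − f)(1 − u)].
- Observed-data difference: −c × (g_T − g_C).

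The documents give none of f, c, w or u, so the values here are assumptions: c = 25, f_C = 5%, u = 10%. To put the true difference at the margin, f_T = 0.05 + 5.1/25 = 25.4%.

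| Failures missing | g_T | g_C | Expected difference | Chance of passing |
|---|---|---|---|---|
| Complete data | 0.254 | 0.050 | −5.1 | 2.5% (nominal) |
| 50% | 0.159 | 0.028 | −3.3 | about 12% |
| 80% | 0.070 | 0.012 | −1.5 | about 40% |

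The last column is by simulation: 47 per arm, SD 8, and an unadjusted t interval in place of the ANCOVA. A repeat with 20,000 trials per setting and u from 5% to 15% gave about 12 to 15% and 37 to 43%.

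**3. Is that much missing data plausible?** With half of the failures missing, 0.254 × 0.5 + 0.746 × 0.10 = 20% of the investigational arm and 0.05 × 0.5 + 0.95 × 0.10 = 12% of the control arm have no score, 16% overall. With 80% missing the figures are 28% and 13.5%, about 21% overall, just over the section 7.4 ceiling. With u = 5% they are 24% and 9%, about 16% overall.

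**4. Other assumptions.** If a failed repair has a mean change of 0 or 17 points instead of 34, control failures are 0 to 10% and nothing else is missing, false passing at a true difference of 5.1 is 2 to 4% with all failures observed, 11 to 23% with half missing and 74 to 84% with all missing. In the simplest case, 15 percentage points more failures with no improvement give 0.15 × 34 = 5.1 points, and 0.15 × 47 is about 7 patients. With the margin of 8 from section 7.5, the three ranges are 2 to 4%, 15 to 32% and 94 to 99.5%.

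**5. Settings where the effect is absent or reversed** (c = 25, margin 5.1; 80% of failures missing unless stated):

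- Failures 10% in both arms: estimate unbiased at 0.0, but passing rises from about 60% to 73% because the low scores no longer widen the interval.
- Failures 5% investigational, 20% control: passing falls from 97% to 84%.
- Failures 20% against 5%, but only 20% of them missing: about 9 to 13% against 9%, little change.

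**The case against.** The strongest reply is that the plan has not adopted complete-case analysis. Section 7.7 reserves imputation for the statistical analysis plan and keeps dropouts in the analysis, and section 7.9 promises a strategy for the FAS. A reader might infer that patients with failed repairs are removed as a settled rule. The documents do not support that: the text is inconsistent and the method deferred, and a failed repair with a recorded 6-month score stays in. Section 13.1.3 lists device removal and reoperation separately from study withdrawal, and nothing says that follow-up stops after them. The PPS loses non-completers through its own definition, not through section 7.7.

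The supporting evidence also has another side. Section 10.2.3 goes on to call withdrawal after device failure less likely, and section 10.1 expects few dropouts. Section 7.8 says that main methods should in principle not change and that changes are recorded, and section 7.6 rules out an interim analysis. Section 7.1.2 plans to compare dropout between groups and list the reasons, so a marked imbalance would be visible.

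The direction of any bias is an assumption. Section 4.2 cites a 22.4% reoperation rate for the Fast-Fix device in bucket-handle tears, so a 5% control failure rate has no anchor in the documents.

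All of this limits the claim but does not remove it. Deferring the method is not specifying it, the section 7.8 safeguard has no missing-data method to protect, and seeing an imbalance does not alter the pass rule.

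**Conclusion.** The point stands in limited form. Observed-data analysis is the only concrete rule, the surrounding statements conflict with it or defer it, and no primary method or sensitivity analysis is pre-specified. If failed repairs with missing scores are more frequent or worse in the investigational arm, non-inferiority is favoured. With an assumed 25-point cost, and the true difference at the 5.1 margin, false passing rises from 2.5% to about 12% with half of the failures missing and about 40% with 80% missing.

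Two stronger readings are tempting and should be resisted.

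- That the plan biases the result towards success. With equal failure rates the estimate is unbiased, though the interval narrows, and with more control failures the effect runs against the device.
- That milder scenarios show false success. With failures of 20% against 5% and 80% of them missing, passing is about 50 to 54% on observed data against 8% on complete data. But the true difference is 0.15 × 25 = 3.75 points, inside the 5.1 margin, so a pass there is a correct conclusion. Those figures show distortion of the estimate, not type I error.

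This should be changed before 6-month data by arm are available. Sections 7.2.1 and 7.5 give different margins (5.1 and 8), which must be reconciled separately.

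**What to change.** Replace the observed-data sentence in section 7.7, and align section 7.9 with it, as follows.

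1. **Primary FAS method.** Name one: a repeated-measures model of Lysholm change at 3, 6 and 12 months adjusted for baseline and centre, with the 6-month contrast as the primary estimate; or multiple imputation that includes the 3-month score.
2. **Sensitivity analyses.** Either primary method assumes data missing at random, so on its own it does not deal with failure-related loss. Add (a) unfavourable imputation of scores missing after device failure or reoperation and (b) a tipping-point analysis that worsens imputed investigational scores until the lower limit reaches the margin. Unfavourable imputation as the primary analysis would be debatable, so it belongs here.
3. **Timing.** Finalise this before anyone sees 6-month data by arm, not merely before database lock.
4. **Decision rule.** State that the pass rule must be met in both FAS and PPS. This settles which set governs, but does not replace items 1 and 2, since both sets can lose the same subjects.

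The cost is plan wording and modest analysis work, with no new data. The downside is a possibly wider or less favourable interval when failures drop out.

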## **7.8 Procedure for reporting deviations from the original statistical plan**

The statistical analysis plan needs to be confirmed by the sponsor, coordinating investigators, data management and statistical analysis personnel, and finalized prior to database locking. Before finalization, the initial analysis plan can be modified according to the actual situation in the trial process. Any change to the original statistical analysis plan due to the changes in the protocol shall be confirmed again by the sponsor, coordinating investigators, data management and statistical analysis personnel, and the change shall be made in strict compliance with the clinical trial operating rules and procedures. In principle, no change will be made to the main analysis principles, methods, and analysis sets, and all changes (if any) shall be recorded.

## **7.9 Selection criteria for subjects included in the analysis and the rationale**

**Full Analysis Set (FAS):** A set of subjects determined according to the Intention To Treat principle, which refers to a data set composed of all subjects who have signed an informed consent form and used the investigational medical device. For subjects whose primary efficacy evaluation is not observed, different strategies will be adopted to intercept the missing data.

**Per-Protocol Set (PPS):** refers to a subset of treatment population who have all finished the trial and have no severe deviation from the protocol (i.e., violations of subjects of the clinical trial against the inclusion criteria or exclusion criteria).

**Safety Set (SS):** refers to the set of all subjects who have signed an informed consent form, used the investigational medical device, and have at least one safety evaluation result.

Efficacy analysis will be performed based on the Full Analysis Set and Per-Protocol Set. All demographic analysis at baseline will be performed based on the Full Analysis Set, and the safety evaluation will be performed on the Safety Set.

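### Section 7.9 ties the FAS and Safety Set to use of the investigational device and the PPS to completing the trial; all three definitions need rewording

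*Combined protocol and SAP*

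**What the plan says.** Section 7.9 defines three sets.

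- **FAS.** It is said to rest on the intention-to-treat principle and consists of "all subjects who have signed an informed consent form and used the investigational medical device". Randomisation is not mentioned.
- **Safety Set.** Subjects must have consented, "used the investigational medical device, and have at least one safety evaluation result".
- **PPS.** It "refers to a subset of treatment population who have all finished the trial" and have no severe deviation. A bracket introduced by i.e. explains severe deviation as "violations of subjects of the clinical trial against the inclusion criteria or exclusion criteria".

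Sections 7.1.2 and 7.9 run the efficacy analysis on both the FAS and the PPS. Section 7.7 treats agreement between the two as adding credibility. Section 7.5 makes the 6-month non-inferiority comparison the pass/fail test for the device.

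**The concern.** An analysis-set definition has to be something a programmer can apply without guessing. Three features of section 7.9 fail that test.

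First, the synopsis lists JuggerStitch as the investigational device and Fast-Fix 360 separately as the control device, so two of the three sets name only one arm's product. Second, a condition of having used a device selects on what happened after randomisation, which does not match the principle claimed for the FAS. No rule covers a subject repaired with a device other than the one assigned. Third, PPS membership depends on finishing the trial rather than on having the primary outcome, and its deviation clause is narrow.

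At stake is who enters the comparison that decides whether the device passes, and whether FAS/PPS agreement means anything.

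**Working it through.** **1. The plan's own sample size.** Inputs from section 7.2.1: mean change 34 in both groups (true difference 0), SD 8, margin 5.1, one-sided alpha 0.025, power 80%.

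n = 2 × (1.960 + 0.842)² × 8² / 5.1² = 38.6, so 39 per group. The noncentral-t version gives 40 (power 80.4%). With 15% dropout, 80 / 0.85 = 94.1, matching the stated 94, or 47 per arm. Nothing proposed below changes this.

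**2. What the device term means.** The synopsis gives the label to JuggerStitch only. Section 13.1.1, first note to the adverse event definition, names the investigational device and the comparator as two things. On a literal reading the FAS and Safety Set hold up to 47 JuggerStitch subjects and 0 of 47 controls. Against that, section 7.1.2 compares baseline characteristics of two groups on the FAS and estimates a between-group difference, and section 7.5 judges that difference. Two arms are plainly intended.

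**3. The sets applied case by case**, reading the device condition as either study device:

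| Subject | FAS | PPS |
|---|---|---|
| Randomised, repaired with neither study device | Out | Out, if drawn from treated subjects |
| Repaired with the non-assigned device, eligible, finishes | In, arm not stated | In, arm not stated |
| Valid 6-month score, leaves at month 9 | In | Out |
| 6-month visit outside the ±30-day window, eligible, finishes | In | In |
| Misses month 6, attends month 12, eligible | In, score missing | In, no primary score |

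The third row arises because sections 6.1.5.5 and 6.1.5.6 set follow-up at 12 months, while the synopsis and sections 5.2.1, 7.1.1 and 7.5 put the primary endpoint at 6 months. The fourth arises because section 14.1, item 4, calls a visit outside its window a deviation but the PPS bracket does not count it.

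**4. Size, FAS.** One subject is 1/47 = 2.1% of an arm. If k JuggerStitch subjects were left out and their mean change was L points below the rest, the arm mean would rise by k × L / 47. The documents give neither k nor L. Assuming k from 1 to 3 and L from 10 to 34 (34 being the whole assumed improvement), the shift runs from 1 × 10 / 47 = 0.2 to 3 × 34 / 47 = 2.2 points, against the 5.1 margin. Similar exclusions in the control arm would offset it.

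**5. Size, PPS.** The documents do not split dropout before and after month 6, so only a range is possible, assuming dropout is the only reason for exclusion.

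- At the 15% of section 7.2.1, 0.15 × 47 = 7.05, so 0 to about 7 valid scores per arm could be lost. It is 0 if every dropout leaves before month 6.
- At the 20% ceiling of section 7.4, 0.20 × 47 = 9.4, so 0 to about 9.
- Power by the t calculation (margin 5.1, SD 8) is 86.4% with 47 per arm, 80.4% with 40 and 78.3% with 38. The cost to the PPS analysis therefore lies between nothing and 86.4 − 80.4 = 6.0 percentage points, or 86.4 − 78.3 = 8.1 at 20%.

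**The case against.** The best defence is that everyone knows what was meant. The two-arm intention is clear from sections 7.1.2 and 7.5, and section 6.1.4, titled for the investigational device, also describes the Fast-Fix 360 technique, so the protocol uses the term loosely. Randomisation takes place during surgery after the arthroscopic eligibility check, and section 6.1.3, item 3, has interventions follow the randomisation result. Few subjects should go untreated or be treated off-allocation. Requiring completion in a PPS is also not wrong in itself. All of this stands, and it limits the size of the problem. It does not supply an arm rule, make a treated set a randomised one, or link the PPS to the 6-month score.

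A reader might infer more than the documents support:

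- **That section 7.7 conflicts with section 7.9** because it says "All subjects shall be included in the analysis of primary indicators". The same sentence goes on to select the FAS and PPS for that analysis, so it does not set up a rival all-randomised population.
- **That the surgeon may choose the device after randomisation**, because section 8.2.2.4 has a probe guide selection of the repair system in the step after randomisation. Section 6.1.3, item 3, points the other way, and Step 2 of the JuggerStitch technique uses a probe to choose between a straight and a curved needle.
- **That the missing-data statements contradict each other.** Section 7.7 says "all analyses will be based on the actual data obtained" and adds "Any filling in the missing primary endpoint indicators will be addressed in the statistical analysis plan"; section 7.9 says "different strategies will be adopted to intercept the missing data". These are compatible if the statistical analysis plan names the strategies. A tipping-point calculation on missing scores would not measure set membership, so none is offered as the size of this point.

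**Conclusion.** Section 7.9 is wrong as written and should be corrected, but the expected numerical effect is small. The absence of controls from the FAS and Safety Set is a drafting error; it would be a mistake to infer that a one-arm analysis is planned. What remains on the sensible reading is a FAS that is a treated set with no arm-assignment rule, and a PPS that can drop subjects who have the primary outcome while keeping subjects who did not receive the allocated device or were assessed outside the window.

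The numbers affected cannot be computed from the documents. They may be few or none, and the ranges shown rest on assumed values of k and L and on an unknown timing of dropout. The PPS point takes 6 months as the primary time. Section 6.1.2 names 12 months instead, and the margin differs between sections 7.2.1 (5.1) and 7.5 (−8); both are separate matters.

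**What to change.** Reword section 7.9 and carry the text into the statistical analysis plan:

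- **FAS:** all randomised subjects, analysed in the arm to which they were randomised.
- **Safety Set:** all subjects treated with either study device, analysed by device received.
- **PPS:** subjects with a valid 6-month Lysholm score who received the allocated device and have no major deviation, in place of trial completion. State which items of section 14.1 count as major. Use of a non-assigned device is not on that list, so it needs its own condition. If loss to follow-up (item 5) is kept, limit it to loss before the 6-month score; otherwise it brings the completion requirement back.
- **Missing scores:** replace the general sentence in section 7.9 with a cross-reference to the method that the statistical analysis plan names under section 7.7.

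This needs no extra subjects, visits or data, and the sample size is unchanged. The cost is minor rewording and programming. Including every randomised subject may slightly widen the FAS interval. Section 7.8 says the analysis sets will in principle not change, so the correction is best made before that plan is final.

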Exclusion Criteria	(1) Patient has meniscal tears in the avascular zone of meniscus; (2) Meniscal tears not suitable for repair because of the degree of damage (marked irregularity and complex tearing) to the meniscus body including degenerative, radial, horizontal cleavage, flap and root tears; (3) Patient with multiple ligament injuries of the affected knee joint; (4) Patient with adhesion of the affected knee joint; (5) Patient is planned to accept intraoperative or postoperative intra - articular injection;

	
 
(6) Articular surface cartilage injury of the targeted knee assessed by the International Cartilage Repair Society (ICRs) is grade 3-4;
 
(7) Kellgren-Lawrence grades of documented radiographic evidence of Osteoarthritis (OA) in the affected knee is <math>\geq III</math>.
 
(8) Instability or valgus/varus deformity(<math>>5^\circ</math>) of the affected knee;
 
(9) Patient has acute or chronic, local or systemic infections;
 
(10) Patient with metabolic diseases;
 
(11) Abnormal liver and kidney function (creatinine 3 times higher than the upper limit of normal value or alanine aminotransferase or aspartate aminotransferase 3 times higher than the upper limit of normal value) before operation;
 
(12) History of operation in the affected knee;
 
(13) Acute myocardial infarction or stroke occurred within 6 months before operation;
 
(14) Patients are known allergy to any material (polyethylene, polypropylene, polyester, polyetheretherketone) of the implants;
 
(15) Patient is pregnant or known to be pregnant;
 
(16) Other circumstances that the researchers believe that may affect the efficacy and safety evaluation of the investigated medical devices;
 
(17) Patients are currently participating in other clinical trials.
 

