#### **8.2.2.5 Postoperative rehabilitation and follow-up visits**

- (1) Postoperative treatment: subjects are recommended to use the elastic bandage round limb, appropriate massage to prevent blood clots. After being awake anesthesia, nurse will provide guidance on quadriceps isometric contraction and the straight leg-raising training. See Appendix 9 Postoperative Rehabilitation Guidance.
- (2) Subjects will be followed up in clinical visits at postoperative 3 months, 6 months and 12 months, and Lysholm Knee Score, Tegner Activity Score, and VAS will be obtained at each follow-up visit to assess the recovery of knee joint.
- (3) MRI of the knee joint will be performed at postoperative 6 months and 12 months to evaluate the recovery of meniscus.
- (4) Monitor and record clinical adverse events during each follow-up period for data evaluation and analysis.
- (5) Record the use of analgesic drugs at discharge and during each follow-up period (name of drug, start/discontinuation date, and daily dose).

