**Appendix 2 Immediate device success rate**

Device success rate refers to the successful suturing of the injured site without any additional instruments (except matching surgical tools) during the operation.

Device Success Rate= Number of successfully implanted anchors/Total number of implanted anchors ×100%

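### Apart from non-completion, the per-protocol set drops only eligibility violators, so a completer repaired with non-allocated fixation stays in and FAS/PPS agreement does not test the effect

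*Combined protocol and SAP*

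**What the plan says.** Section 7.9 restricts the PPS to treated subjects who completed the trial and who "have no severe deviation from the protocol (i.e., violations of subjects of the clinical trial against the inclusion criteria or exclusion criteria". There are thus two conditions: completion and eligibility.

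Section 14.1 has a wider list of seven protocol deviations, covering eligibility, consent, missed tests, visits outside the window, loss to follow-up, SAE reporting and GCP violations. None concerns the treatment received, and section 7.9 does not refer to the list.

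On treatment received, section 6.1.3 states that "Interventions will be performed on the subjects according to the randomization results obtained by the central randomization system". The surgical procedure (section 8.2.2.4) randomises at item (4), has the surgeon choose the suitable repair system with the probe at item (5), and records the devices used at item (6). Appendix 2 defines device success as "successful suturing of the injured site without any additional instruments (except matching surgical tools) during the operation".

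On injections, exclusion criterion (5) reads "Patient is planned to accept intraoperative or postoperative intra - articular injection". Item (5) of the follow-up section (8.2.2.5) is limited to analgesics: "Record the use of analgesic drugs at discharge and during each follow-up period".

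On the use of the two sets, section 7.7 says: "When the analysis conclusions of the above two data sets are consistent, the credibility of the study results can be enhanced". Section 7.8 adds that the analysis sets will in principle not be changed.

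**The concern.** In a non-inferiority trial the per-protocol analysis is normally read as the comparison of the devices as actually used, alongside the comparison as randomised. That is general statistical reasoning; section 7.7 does not state it. The reading works only if the PPS requires that the allocated device was used.

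Here it does not. A JuggerStitch subject whose repair was completed with Fast-Fix 360 or another fixation, and who attends all visits, counts as per-protocol JuggerStitch. The same subject is normally in the FAS too. Agreement between the two sets then shows that non-completers and eligibility violators did not drive the result. It does not show whether mixed treatment did.

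If the rule is not set in advance, any later exclusion has to be decided case by case. Section 6.1.3 lists no blinding among its measures against bias, so those deciding may know both allocation and outcome.

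**Working it through.** **Reading the definition.** Section 7.9 uses i.e., not e.g., so eligibility violation is the whole meaning of severe deviation rather than an example. Applied to completers:

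- Ineligible at entry, including an injection already planned (exclusion 5): removed.
- Eligible, index tear fixed wholly or partly with a non-allocated device: no rule removes the subject.
- Eligible, intra-articular injection not planned at enrolment: no rule removes the subject.

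**The plan's own figure.** Inputs from section 7.2.1: margin 5.1, SD 8, true difference 0, one-sided alpha 0.025, power 80%.

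- Normal approximation: 2 × (1.960 + 0.842)² × 8² / 5.1² = 38.6, so 39 per arm. The t-based calculation gives 40 (power 80.4%).
- With 15% dropout: 80 / 0.85 = 94.1, against the stated 94. The sample size reproduces and is not in dispute.

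**Illustration of false passing.** Further assumptions, not in the documents: a share f of test-arm knees is rescued, none in the control arm, and rescue removes the whole deficit. The true deficit of the device used alone equals the margin M.

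- SE = 8 × √(2/40) = 1.789
- Expected observed deficit = M(1 − f)
- P(pass) = 1 − Φ(1.960 − M f / 1.789)

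| f | M = 5.1 (section 7.2.1) | M = 8 (section 7.5) |
|---|---|---|
| 0 | 2.5% | 2.5% |
| 10% (4 of 40) | 1 − Φ(1.675) = 4.7% | 1 − Φ(1.513) = 6.5% |
| 20% (8 of 40) | 1 − Φ(1.390) = 8.2% | 1 − Φ(1.066) = 14.3% |

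**The direction depends on the assumption.** Suppose instead that rescued test knees do worse and have twice the deficit. The expected deficit becomes 5.1(1 + f), and P(pass) = 1 − Φ(1.960 + 5.1 f / 1.789). This is 1 − Φ(2.245) = 1.2% at 10% and 1 − Φ(2.530) = 0.6% at 20%. Keeping these knees then works against the test device. Helpful rescue in the control arm also works against it.

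**Cost of exclusion.** Margin 5.1, true difference 0:

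- No exclusion: Φ(5.1/1.789 − 1.960) = 81.4%.
- 10% of the test arm removed (36 v 40): SE = 8 × √(1/36 + 1/40) = 1.838; Φ(5.1/1.838 − 1.960) = 79.2%.
- 10% removed from both arms (36 v 36): SE = 8 × √(2/36) = 1.886; Φ(5.1/1.886 − 1.960) = 77.2%.

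**The case against.** **Departures may be rare.** Section 6.1.3 requires treatment according to randomisation, and section 20.2 requires strict adherence to the protocol. Appendix 2 defines what counts as success; it does not predict failures or name a rescue device. This stands as far as frequency goes: the documents support no rate. It does not answer the definition, because a departure that does occur has no stated consequence for the PPS.

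**Excluding rescues can itself bias the PPS.** Added fixation happens after randomisation and may be caused by failure of the allocated device. Removing such knees could leave mainly the successes and favour the test device. This stands, and it shapes the fix.

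**A full switch may already fall outside the FAS.** Section 7.9 bases the FAS on use of the investigational device. Read literally, a JuggerStitch-allocated knee repaired wholly with Fast-Fix 360 is not in it. This also stands: the FAS wording has to be amended together with the PPS. Mixed repairs are in both sets on any reading.

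**Injections may be captured elsewhere.** Section 13.1.4 records actions taken for adverse events, and section 9 plans verification of medication and deviations. In part this stands. However, section 13.4 drops adverse events judged unrelated, so capture is possible but not assured.

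**Stronger readings a reader might infer, which the documents do not support:**

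- That the PPS removes nobody except eligibility violators. It also removes non-completers.
- That every injected knee stays in. A planned injection breaches exclusion (5), so that subject leaves the PPS.
- That FAS and PPS must agree almost automatically. With expected dropout of 15% (section 7.2.1) or up to 20% (section 7.4), about 14 to 19 of 94 subjects could separate the two sets.
- That rescue necessarily favours non-inferiority. That depends on the arm in which it occurs and on how rescued knees fare.

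**Conclusion.** The point holds for the treatment actually received. As written, and apart from non-completion, the PPS removes only eligibility violators. Completers with wholly or partly non-allocated fixation remain, and consistency of FAS and PPS carries no information about their effect.

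The size is unknown. The rise from 2.5% to 4.7% or 8.2% rests on illustrative shares of 10% and 20%, rescue in the test arm only, full restoration of the outcome, SD 8, 40 per arm and the 5.1 margin. With the margin of 8 it would be 6.5% or 14.3%. Sections 7.2.1 and 7.5 must be reconciled before any such figure can be relied on. No calculation was made for injections, where the gap is one of assured recording and a planned analysis.

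This should be corrected before database lock. It does not show that the trial's conclusion would be wrong.

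**What to change.** 1. In section 7.9, add to the PPS-excluding deviations any fixation of the index tear with something other than the allocated device, and add the same item to section 14.1.
2. State that these subjects stay in the FAS in their randomised arm, and amend the FAS condition on device use so that it does not drop them.
3. List the excluded knees by arm with the reason, and report a sensitivity analysis that keeps device-failure rescues in.
4. Extend follow-up item (5), in the Synopsis and in section 8.2.2.5, to record any unplanned intra-articular injection of the index knee before the 6-month score (agent and date). Examine these subjects in a sensitivity analysis rather than by mandatory PPS exclusion. This concerns recording and analysis only, not whether an injection may be given.
5. Reconcile the margin between sections 7.2.1 and 7.5.

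The cost is protocol and SAP wording and one CRF line, since the devices used are already recorded. The PPS becomes slightly smaller, as shown above. The remaining downside is selection if rescues reflect device failure, which is why the FAS and the sensitivity analysis must be reported beside the PPS.
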